## **2.4. Procedures**

### **2.4.1. Subject Identification**

Once consent is obtained and study eligibility has been determined, a subject will be enrolled into the study and will be assigned a Participant Identification (PID) number. The 5-digit PID number will consist of a 2-digit site number and a 3-digit sequential subject number. Note: The protocol allows subjects who completed the IVP portion of the study to re-enroll into the IM portion of the study. For the purpose of analysis, the IM and IVP portions will be treated as separate studies, and new PIDs will be assigned. However the CDISC rules for subjects with multiple enrollments will be applied with regard to the variables. USUBJID (the same across all studies/enrollments) and SUBJID (unique to each study/enrollment).

### **2.4.2. Randomization**

This will be an open-label, non-randomized study.

#### **2.4.3. Blinding/Unblinding**

There will be no blinding/unblinding considerations for this open-label, non-randomized study.

#### **2.4.4. Replacement**

If a subject in the study is discontinued due to any reason other than safety as detailed in Section 4.3 (Safety Monitoring and Toxicity Management Plan) of the study protocol, another subject may be enrolled to replace the lost subject to achieve a total of 20 subjects successfully completing participation in the study.

Study participants who:

1. miss 2 consecutive visits or
2. have more than one treatment visit out of window or
3. have 3 non-treatment visits over 4 weeks that are out of window will be discontinued from the study and replaced.

### **3. Statistical Analysis Considerations**

#### ***3.1. Sample Size***

Anticipated enrollment in the IM portion is 20 subjects from 4 sites in the United States.

#### ***3.2. Analysis Populations***

##### **3.2.1. Intent-to-Treat (ITT) Population**

The ITT population is defined as all subjects enrolled into the study. Subject disposition will be based on the ITT population. The ITT Analysis Set will be used for the AUC and trough serum drug concentration and the secondary effectiveness analysis (assessment of the HIV-1 viral loads).

##### **3.2.2. Safety (SAF) Population**

All subjects who receive at least one partial dose of study drug will be included in the SAF Population. Subjects will be analyzed according to the treatment (dose regimen) they actually received. The SAF Population will be used for the safety analyses.

#### ***3.3. Data Handling***

##### **3.3.1. Measurement Times**

The nominal visit time point entered on the electronic case report forms (eCRFs) will be used. Subjects are asked to adhere to the following visit schedule:

**IM HIV infected Group**

- Study drug administration visits with safety assessments will take place once every two weeks beginning at Day 1 and continuing through Day 85 (12 weeks).
- IM HIV infected Group subjects will be asked to return for the final study assessments indicated for the EOS and Follow-up visits at Days 85 (12 weeks) and 99 (14 weeks), respectively. Subjects who are discontinued or who withdraw from the study prematurely are also requested to complete the assessments for these two study visits. (Refer to the Schedule of Events tables in the protocol for details on procedures for each scheduled study visit and for PK sampling time points.)

**IM HIV uninfected Group**

- Study drug administration visits with safety assessments will take place once every two weeks beginning at Day -55 and continuing through Day 71 (10 weeks).
- IM HIV uninfected Group subjects will be asked to return for the final study assessments indicated for the EOS and Follow-up visits at Days 99 (14 weeks) and 113 (16 weeks), respectively. Subjects who are discontinued or who withdraw from the study prematurely are also requested to complete the assessments for these two study visits. (Refer to the Schedule of Events tables in the protocol for details on procedures for each scheduled study visit and for PK sampling time points.)

**3.3.2. Clinical Laboratory Data Handling Conventions**

If a subject has multiple results in the clinical laboratory data for the Screening visit, only the last result prior to the first dose of study drug will be included in the analysis. If a subject has multiple results (retests) for subsequent visits, the retest results will only be included in the analysis if the subject does not have a value recorded for the original assessment at the given visit.

**3.3.3. Baseline Values**

Baseline is defined as the last assessment prior to the first dose of study drug (Day 1 for all HIV infected subjects, Day -55 for HIV uninfected subjects).

**3.3.4. Missing Data Conventions**

Subjects with missing data at Baseline will use the last Screening visit value as their Baseline result. Unless otherwise specified, missing data for subsequent visits will be considered missing at random and will not be imputed. If necessary, imputation of partial dates may be performed during the data analysis and will be documented (e.g., missing month=July; missing day=15).

### **3.4. Statistical Methods**

#### **3.4.1. General Overview and Plan of Analysis**

The data collected are intended primarily for clinical review and interpretation. The analysis of study data will be primarily descriptive, with emphasis on tabular and graphical displays. Descriptive statistics will be used to guide decisions as to the clinical relevance of findings. Unless otherwise stated, p-values will be determined only if they appear to be warranted from the summary statistics.

Where applicable, summaries will be displayed in the following subject groupings:

- IM HIV infected
- IM HIV uninfected
- Total

In addition, the safety and efficacy summaries will present results grouped by analysis periods, where applicable:

- IM HIV infected: Initial Period (15 min IV Infusion); Investigational Period (IM Injection); Follow-up Period (15 min IV Infusion)
- IM HIV uninfected: Pre-Steady State + IV Infusion Period; Investigational Period (IM Injection); Follow-up Period

For continuous data, descriptive statistics will be presented as number of subjects (n), mean, standard deviation, median, minimum, and maximum. For categorical data, the frequency and percentage of subjects in each category will be presented. Percentages will be based on non-missing data unless otherwise specified.

Data collected during this study will be assigned to the appropriate Analysis Phase, Analysis Period, and Analysis Sub period (where applicable) in which it occurred. The assignment will be based on the visit date, or in the case of cumulative data such as AEs and concomitant procedures, based on the start date. Tables, listings, and graphs will reflect the assignments. A complete description of the phases, periods, and sub periods for the HIV infected and HIV uninfected groups can be found in Appendix 1.

Data will be described and analyzed using the SAS System Version 9 (SAS Institute Inc., Cary, NC, SAS System). Individual subject data will be presented in subject data listings.

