#### IM Group: HIV uninfected subjects

The HIV uninfected subjects in the IM Group (subject numbers XX-601 – XX-6nn) will be enrolled.

**Pre-Steady State Phase:** Subjects will receive a 2000 mg infusion over 60 minutes on Day minus 55 followed by 3 doses of 800 mg infusion over 15 minutes on Days minus 41, 27, and Day minus 13. On Day 1 the subjects will enter the Study Treatment Phase.

**Study Treatment Phase:** HIV uninfected subjects in the IM Group will receive the first two doses of Trogarzo® in accordance with the prescribing information (diluted in 250 mL normal saline and administered over 15 minutes via IVI) at Day 1 and again at Day 15. The next four doses of Trogarzo® will be administered as an IM injection. HIV uninfected subjects will discontinue dosing after the Day 71 study drug administration.

All HIV infected study subjects in both Groups will be observed for 15 minutes after each study drug administration, and HIV uninfected subjects will be observed for 60 minutes. All adverse events (AEs) will be recorded. Vital signs will be measured and recorded at the beginning and end of this observation period.

For the PK profile of Trogarzo® following IM administrations, pre-dose samples will be collected at selected time points, along with samples at 2, 7, 10, and 14 days post-dose for the last two doses of study drug (via IVI), and for the last two IM injection doses for all subjects.

[figure not shown]

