##### **4.3.1. Extent of Study Drug Exposure**

Summary statistics will be presented for the cumulative dose (mg) and duration of treatment received by the subjects in the SAF Population. Duration of treatment will be represented as number of days from first dose of study drug. Corresponding listings will also be generated for study drug administration.

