**Table 14.3.2.1**  
**Abnormal Laboratory Results by DAIDS Toxicity Grade [1] and Route of Administration**  
**Safety Population - IM HIV Infected Group**

Test/Route of Administration [2]	IM HIV Infected (N=XX)				
	Grade 0 n (%)	Grade 1 n (%)	Grade 2 n (%)	Grade 3 n (%)	Grade 4 n (%)
Analyte 1					
IV Infusion (Day 1 - Day 29)	n (xx.x%)	n (xx.x%)	n (xx.x%)	n (xx.x%)	n (xx.x%)
IM Injection (Day 30 - Day 85)	n (xx.x%)	n (xx.x%)	n (xx.x%)	n (xx.x%)	n (xx.x%)
Follow-up (Day 86 - Day 99)	n (xx.x%)	n (xx.x%)	n (xx.x%)	n (xx.x%)	n (xx.x%)
Analyte 2					
IV Infusion (Day 1 - Day 29)	n (xx.x%)	n (xx.x%)	n (xx.x%)	n (xx.x%)	n (xx.x%)
IM Injection (Day 30 - Day 85)	n (xx.x%)	n (xx.x%)	n (xx.x%)	n (xx.x%)	n (xx.x%)
Follow-up (Day 86 - Day 99)	n (xx.x%)	n (xx.x%)	n (xx.x%)	n (xx.x%)	n (xx.x%)

N= All Subjects enrolled (displayed according to assigned treatment) and denominator for percentage calculations.

[1] If a subject reported more than one abnormal result for a given analyte at any point during the study, only the result with the highest grade is counted.

[2] Indicates the route of administration by which the subject was receiving study drug at the time the laboratory result was recorded.

*Note to programmer: 1) Use TRTA to create the rows within each analyte. 2) For each value of PARAMCD select the highest grade for each subject, regardless of visit or period. 3) Count the frequency by analyte, period, and grade.*  
*Only include analytes with abnormal results in the data in this table.*

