**Table 14.3.1.2.3**  
**Overall Incidence of Treatment-Emergent Adverse Events**  
**Safety Population - Core HIV-uninfected Group**

Body System	Preferred Term [1]	Core HIV-uninfected Group (N=XX)				Total	
		Investigational Period		30 sec IV Push	Follow-up Period		
		Pre-Steady State + IV Infusions Period	30 sec IV Push				
Overall[2]	ALL TERMS Events	n (xxx.x%) n	n (xxx.x%) n	n (xxx.x%) n	n (xxx.x%) n	n (xxx.x%) n	
XXXXXXX	ALL TERMS Events	n (xxx.x%) n	n (xxx.x%) n	n (xxx.x%) n	n (xxx.x%) n	n (xxx.x%) n	
	XXXXX Events	n (xxx.x%) n	n (xxx.x%) n	n (xxx.x%) n	n (xxx.x%) n	n (xxx.x%) n	
	XXXXX Events	n (xxx.x%) n	n (xxx.x%) n	n (xxx.x%) n	n (xxx.x%) n	n (xxx.x%) n	
	XXXXX Events	n (xxx.x%) n	n (xxx.x%) n	n (xxx.x%) n	n (xxx.x%) n	n (xxx.x%) n	
XXXXXXX	ALL TERMS Events	n (xxx.x%) n	n (xxx.x%) n	n (xxx.x%) n	n (xxx.x%) n	n (xxx.x%) n	
	XXXXX Events	n (xxx.x%) n	n (xxx.x%) n	n (xxx.x%) n	n (xxx.x%) n	n (xxx.x%) n	

N = All subjects in the Safety Population (displayed according to actual treatment received), and denominator for percentage calculations.

NOTE: Identical TEAEs are counted only once per subject.

[1] "ALL TERMS" represents number(%) of subjects with at least one TEAE within that Body System;

"Events" represents number of TEAEs reported by the subject(s).

[2] Number(%) of subjects with at least one TEAE in any Body System.

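### By-period adverse event tables for the IM and Core Groups set infusion and IM/push columns of unequal length side by side with no exposure-adjusted rate

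*SAP*

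**What the plan says.** The IM SAP, section 3.4.1, groups safety summaries by analysis period. For HIV-infected subjects the listed periods are "IM HIV infected: Initial Period (15 min IV Infusion); Investigational Period (IM Injection); Follow-up Period (15 min IV Infusion"). For volunteers they are "IM HIV uninfected: Pre-Steady State + IV Infusion Period; Investigational Period (IM Injection); Follow-up Period". Adverse events are placed in a period, "in the case of cumulative data such as AEs and concomitant procedures, based on the start date".

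The merged volunteer period starts well before Day 1. IM SAP 2.1 states: "Subjects will receive a 2000 mg infusion over 60 minutes on Day minus 55 followed by 3 doses of 800 mg infusion". The Day 1 and Day 15 infusions follow. The IV push SAP uses the same merged column, "Pre-Steady State + IV Infusions Period", for uninfected Core subjects (mock Table 14.3.1.2.3). A note in its Appendix 1 acknowledges that the first infusion in that period differs in dose and duration from the others.

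The by-period AE tables in both SAPs (14.3.1.1.x to 14.3.1.4.x) print numbers and percentages of subjects. From 14.3.1.2.x on they also print event counts. The footnotes make the whole Safety Population the denominator in every column.

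Neither SAP plans a rate per dose or per unit of time. Exposure is planned as overall totals only (IM SAP 4.3.1; IV push SAP 4.3.1 reads the same): "Summary statistics will be presented for the cumulative dose (mg) and duration of treatment received by the subjects in the SAF Population".

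**The concern.** A percentage of subjects with at least one event rises with observation time and with the number of administrations. When neighbouring columns differ in both, part of any difference between them is due to the schedule rather than the route. Here the imbalance runs in opposite directions in the two HIV strata. With no route effect at all, IM or push could look worse than infusion in HIV-infected subjects and better than infusion in volunteers. A reader might take that pattern as a route effect in each stratum, or as a sign that HIV status modifies one.

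For volunteers, the merged column also combines the 800 mg 15-minute infusion with a 2000 mg 60-minute infusion given at first exposure. The IM SAP's own laboratory toxicity table for the same volunteers (14.3.2.2) leaves the pre-steady-state phase out. Their AE and laboratory results therefore use different infusion comparators.

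**Working it through.** **1. Period lengths.** The inputs are the dosing days in IM SAP 2.1 and IV push SAP 2.1, and the row labels of IM Tables 14.3.2.1 and 14.3.2.2: "IV Infusion (Day 1 - Day 29") and "IM Injection (Day 30 - Day 85"). The IM period runs from Day 29 to Day 85: 85 − 29 = 56 days = 8 weeks. This reproduces the 8 weeks of IM dosing stated in the preference question (IM SAP 4.4).

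- HIV-infected, infusion: Day 1 to Day 29, 29 − 1 = 28 days; doses on Days 1 and 15 (2 doses).
- HIV-infected, IM or push: 56 days; doses on Days 29, 43, 57 and 71 (4 doses).
- Uninfected, merged infusion column: doses on Days −55, −41, −27, −13, 1 and 15 (6 doses). Six 14-day intervals to Day 29 give 84 days, or 83 if there is no Day 0.
- Uninfected, IM or push: 56 days, 4 doses.
- Sentinel: infusion on Days 1 and 15, to Day 29, 28 days; push on Days 71 and 85, to Day 99, 99 − 71 = 28 days. Balanced.

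**2. Expected event-count ratio, IM/push to infusion, at equal rates.** HIV-infected: 56/28 = 2.00. Uninfected: 56/84 = 0.67. Doses give the same ratios: 4/2 = 2.00 and 4/6 = 0.67.

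**3. Expected percentage of subjects with an event.** Assume a constant rate, the same on both routes, with a share p of subjects having an event per 28 days. Then P(28) = p, P(56) = 1 − (1 − p)², and P(84) = 1 − (1 − p)³. The documents give no value for p, so a range is shown.

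| p per 28 days | 28 d | 56 d | 84 d | Infected, 56 d/28 d | Uninfected, 56 d/84 d |
|---|---|---|---|---|---|
| 5% | 5.0% | 9.8% | 14.3% | 1.95 | 0.68 |
| 10% | 10.0% | 19.0% | 27.1% | 1.90 | 0.70 |
| 20% | 20.0% | 36.0% | 48.8% | 1.80 | 0.74 |
| 30% | 30.0% | 51.0% | 65.7% | 1.70 | 0.78 |
| 50% | 50.0% | 75.0% | 87.5% | 1.50 | 0.86 |

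For p = 20%: 1 − 0.8² = 36.0% and 1 − 0.8³ = 48.8%.

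**4. An anchor from the protocol.** Protocol 1.2 reports that 80% of subjects in the previous 24-week Phase 3 study had any treatment-emergent event. Spread evenly over 168 days (an assumption), P(d) = 1 − 0.2^(d/168). This gives 23.5% at 28 days, 41.5% at 56 days and 55.3% at 84 days. HIV-infected subjects would show 23.5% on infusion against 41.5% on IM/push (+18.0 points), and volunteers 55.3% against 41.5% (−13.8 points). For treatment-related events (17.5% in that study), the figures are 3.2% against 6.2%, and 9.2% against 6.2%.

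**5. What a rate does.** At p = 20%, expected events per subject are −ln(0.8) = 0.223 in 28 days, 0.446 in 56 days and 0.669 in 84 days. Per 100 subject-weeks: 0.223/4, 0.446/8 and 0.669/12 all give 5.6. Per 100 doses: 0.223/2, 0.446/4 and 0.669/6 all give 11.2. The false difference disappears in both strata.

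**6. Splitting the volunteer column alone.** This leaves 28 against 56 days and a count ratio of 2.00, so it is not sufficient without a rate. Table 14.3.2.2 is already in this position: it leans towards an IM excess, not a deficit.

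**The case against.** Several arguments limit the point.

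- A reader might infer that the tables cannot answer the primary safety objective. The documents do not support this. The objective is to evaluate the safety of the new route and names no infusion reference; only the PK objectives ask for a comparison. No safety test or margin is planned, and the analysis is descriptive. But the design text (protocol 3.2, IM SAP 2.1, IV push SAP 2.1) does set safety on the new route against the approved infusion, so the side-by-side reading is one the documents invite.
- A reader might take the by-period AE tables to be the only safety comparison of routes. They are not: IM Tables 14.3.2.1 and 14.3.2.2 give laboratory toxicity by route, and vital signs and physical findings are also shown by period.
- A reader might extend 28 against 56 days to every HIV-infected subject. The Sentinel Group is an exception, with 28 days on each. Only its intermediate steps are shorter, at 14 days, and these are not the infusion-versus-push contrast.
- Event counts are printed, doses per period are fixed by design, and the listings carry AE start days and dosing dates. A careful reader could divide approximately. This stands in part, but the column headings show neither days nor doses, and a subject who leaves before the first IM or push dose still counts in that column's denominator.
- Events may not occur at a constant rate, and injection-site reactions have no infusion counterpart. This stands, and the percentages are illustrations. For volunteers, events clustered at first exposure would fall in the merged infusion column and enlarge the apparent deficit.
- Rates do not remove the fixed infusion-then-IM/push order of an open-label, non-randomised design. This also stands.

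**Conclusion.** The concern holds for the by-period AE tables of the IM Group and the Core Group. The columns cover 28 against 56 days in HIV-infected subjects and about 84 against 56 days in uninfected subjects, with a common denominator and no exposure-adjusted rate. Under equal and roughly constant rates, the expected count ratios are 2.0 and 0.67. For an assumed 5% to 50% of subjects with an event per 28 days, the ratios of percentages run from 1.95 to 1.50 and from 0.68 to 0.86.

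These are expected artefacts under a model, not predictions of what the trial will show. Stated without the constant-rate condition, the claim of a false excess and a false deficit would go too far. It also does not carry over to Sentinel infusion against push, or to the uninfected laboratory toxicity table.

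The period limits used for AEs are inferred from the dosing days and the IM laboratory tables, because the figures that define the analysis periods are not shown in the available text. The merged volunteer column itself is explicit in both SAPs. The display should be changed because it can mislead and the correction is cheap.

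**What to change.** In the by-period AE tables of the IM SAP and the Core by-period AE tables of the IV push SAP:

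1. For uninfected subjects, show the pre-steady-state phase (Day −55 to Day 1) separately from the 800 mg 15-minute infusion period (Day 1 to Day 29). This matches the comparator already used in IM Table 14.3.2.2.
2. Beside n (%), print events per 100 doses and events per 100 subject-weeks at risk for each period, counting only subjects and time actually in that period.
3. In the study drug administration tables (IM 14.3.5.1, IV push 14.4.1), report doses and days of exposure by route. Base any descriptive statement on AEs under infusion against IM or push on the rates, and note the constant-rate assumption and the fixed order of routes.

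The cost is edits to table shells and two derived denominators from dosing and AE dates already collected. The tables become wider, and with about 20 subjects per route the rates will be imprecise, so they should stay descriptive.

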## **4. Statistical Analysis**

### **4.1. Subject Disposition**

The number of subjects in the ITT and SAF Populations will be tabulated.

Study completion data will be summarized for all enrolled subjects. The number and percent of subjects who complete treatment; discontinue study medication prematurely; or discontinue the study prematurely will be tabulated. The primary reason for premature discontinuation of study medication and/or discontinuation from study participation will be tabulated. Any additional reason(s) for premature discontinuation of study medication will also be tabulated. A listing of all enrolled subjects will be provided.

#### ***4.2. Demographic and Physical Characteristics***

Summary statistics will be presented for demographic and other Baseline characteristics for the ITT Population. Tabulations for age, sex, ethnicity (Hispanic/Latino, Not Hispanic or Latino, Unknown), and race (American Indian/Alaska Native, Asian, Black/African American, Native Hawaiian/Other Pacific Islander, White, Unknown, or Other) will be presented. Age (years) will be calculated as the integer part of [(date of screening - date of birth + 1)/365.25]. Baseline physical characteristics, such as height (cm) and weight (kg), will also be summarized.

A listing of demographic and Baseline characteristics will be presented, as well as a listing of medical history.

#### ***4.3. Analysis of Safety and Tolerability***

Safety and tolerability will be assessed by both clinical and laboratory examinations. Summary statistics will be presented by AEs; hematology and serum chemistry; vital signs, and abnormal physical examination findings in the SAF Population. Clinical laboratory values outside the normal ranges will be flagged in subject data listings. Non-numeric data will be presented in subject data listings, but will not be summarized.

##### **4.3.1. Extent of Study Drug Exposure**

Summary statistics will be presented for the cumulative dose (mg) and duration of treatment received by the subjects in the SAF Population. Duration of treatment will be represented as number of days from first dose of study drug. Corresponding listings will also be generated for study drug administration.

##### **4.3.2. AEs**

All AEs will be coded using MedDRA dictionary version 22.0. The use of another version will not be considered a violation of the SAP, nor require an amendment to the plan. All summary tables will be based on coded preferred terms (PTs), instead of verbatim terms. The categories and definitions of severity and causal relationship for

all AEs, including the criteria for which an AE is to be classified as “serious,” are as described in the protocol (Section 8).

A treatment-emergent AE (TEAE) is defined as any event not present before exposure to study drug or any event already present that worsens in either intensity or frequency following exposure to study drug. All AEs entered on the Adverse Events eCRF will be analyzed as TEAEs. A TEAE with missing severity or relationship will be considered severe or related, respectively.

The overall incidence of TEAEs will be summarized for all subjects in the SAF Population. The number and percentage of subjects having the following will be tabulated:

- TEAE
- Serious TEAE
- TEAE leading to discontinuation
- TEAE with outcome of death
- Suspected Adverse Reaction
- Severe (Grade 3 or 4) TEAE
- Class C TEAE per the Centers for Disease Control and Prevention (CDC) Classification System for HIV Infection

The overall incidence of TEAEs will also be summarized by System Organ Class (SOC), and by SOC and PT. The number and percentage of subjects reporting an event, as well as the number of events reported by the subjects will be tabulated. The incidence of serious TEAEs and TEAEs leading to study discontinuation (if any) will be summarized in the same manner. If there are multiple occurrences of the same TEAE within any SOC or PT for the same subject, only the first occurrence will be counted.

The incidence of TEAEs by severity/grade (Mild, Moderate, Severe, or Potentially life-threatening, Death) and by relationship to study drug (Suspected Adverse Reaction or Unrelated), and the incidence of serious AEs (SAEs) by relationship to study drug, will also be summarized.

All other AEs will be classified as non-TEAEs and identified in listings only. Serious TEAEs, TEAEs leading to study discontinuation, and TEAEs with an outcome of death will be presented in separate listings, if needed.

